* ≥ 2 mm net wheal or specific IgE ≥ 0.35		

Professional IPM will be delivered by a local pest management company using protocols we have developed for other studies. For rodents, the intervention will include placement of traps, application of rodenticide in cracks and sealing of cracks and holes that can serve as an entry point for rodents. For cockroaches, the intervention will be based on previous successful protocols^(22, 24) and will include placement of Advion (indoxacarb), a low-toxicity gel bait, and sticky traps for monitoring of cockroach infestation. Indoxacarb is the active ingredient in pesticides used on pomme fruits such as apples and in products used to kill fleas on cats and dogs. It is a commercially available pesticide for cockroach control and will be applied by licensed exterminators according to the manufacturer’s instructions.

Parents/guardians will be asked to place the sticky traps 3-4 days prior to the IPM visit so that the location(s) of cockroach activity can be accurately identified. They will be given detailed instructions along with the sticky traps. The study team may assign a team member to place the traps for the family if this seems necessary. If for some reason, traps are not placed prior to the intervention visit the IPM team may place the traps and return to the house after 3-4 days for the placement of gel bait. The IPM team will count the number of cockroaches caught on the sticky traps and use a vacuum as a cockroach removal tool. The local pest management company, Innovative Pest Management, provides protocolized IPM services for a current study. As many as four IPM visits may occur for persistent or recurrent infestation. If new evidence of mouse or cockroach is seen or reported any time between HV1 and INT 3, the appropriate module will be completed in the home before CV3.

Allergen-proof mattress and pillow encasements will be installed by study staff. These encasements block particles down to 1 micron in size so are optimal for blocking allergens such as furry animal allergens that are found on smaller particles than dust mite and cockroach allergens.

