Targeted cleaning will be included in all allergen-related modules. Targeted cleaning will take place at Intervention 1 and 4. For the rodent and cockroach modules, cleaning will focus on removing allergen reservoirs and cleaning areas that have the greatest pest activity, such as the kitchen. For the furry pet and dust mite modules, the targeted cleaning will focus on the child's bedroom with the goal of reducing allergen levels in the bedroom.

IPM Education will focus on counseling participants about storage of food and housekeeping practices aimed at reducing food and water sources for pests. Participants receiving the rodent module will be provided an IPM kit that includes traps and other supplies so that families can implement IPM measures in addition to the professional IPM services that are provided.

Replacement Bedding will be included in all modules. The study will provide bedding (sheets, pillowcases, and comforter) to the participant throughout the study. The child's bedding will be replaced at Intervention 1 and 3 with bedding provided by the study. The participant's bedding will be removed from the bed and replaced with study bedding at Intervention 1. At Intervention 3 the study bedding will be removed and replaced with another set of study bedding. At Home Visit 3 the study bedding will be removed and replaced with the participant's original bedding. All study bedding will be laundered by the JHH laundering facility after it is removed from a home before being deployed to another participant. Families will also be counseled to wash all of the child's bedding in the hot water cycle every 1-2 weeks.

Furry pet and dust mite education will be delivered by study staff. For pets, it will focus on encouraging the family to find the pet a new home or, at the least, to restrict the areas of the home that the pet can be in, particularly the child's bedroom. For dust mite and furry pets, families will be counseled to wash all of the child's bedding in the hot water cycle every 1-2 weeks.

SHS Education will include provision of resources for smoking cessation and tools and support for instituting a home smoking ban.

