participants. All databases will be kept on a network drive, and permissions for this drive can be controlled to allow only study staff to have access to the databases. The drive is backed up twice daily. Only study staff trained in phlebotomy will perform venipuncture, and the questionnaires, spirometry, eNO, and urine collection for cotinine will be collected by a trained research assistant. Home visits and collection of environmental samples will be collected by a trained research technician. Extermination procedures will be performed by a trained and licensed pest exterminator. Skin testing will be supervised by the Study Coordinator or PCRU nurse who will have direct access to the study physician. Appropriate medications, including antihistamines and epinephrine will be immediately available during all of the skin testing procedures. In addition, a short acting beta agonist will be available.

An independent Data Safety Monitoring Board (DSMB) will be populated by experts in clinical trials, data and safety monitoring, and asthma. The DSMB will review the protocol prior to beginning the trial. In addition, the DSMB will meet annually to review accrual and adverse events.

The DSMB will review any event as requested by the Investigators or the sponsor. They will review the study annually, including accrual and adverse events and submit a report following their meeting. Related adverse events and serious adverse events, whether deemed related to study procedures or activities or not, will be tracked.

There will also be weekly meetings of the investigators and study staff, which will include an update of all related adverse events and drop-outs. All serious adverse events will be reported in an expedited manner to the IRB. All unexpected and related serious adverse events will be reported to the DSMB per their request.

c. Plan for reporting unanticipated problems or study deviations.

Unanticipated problems or study deviations will be reported to the IRB and DSMB in an expeditious manner, in adherence with institutional policies.

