Adverse events will be documented on an individual adverse event log for each participant. An adverse event form will be used for reporting all related adverse events. An additional form will be required for serious adverse events to collect additional information. Information that will be documented includes a brief description of the event, onset and duration of the event, severity/grade of the event, resolution status of the event, and relatedness to the study procedures. Any medical intervention will also be documented.

A serious adverse event (SAE) is defined as any adverse experience that suggests a significant hazard, contraindication, side effect, or precaution. This includes, but may not be limited to, any of the following events:

1. Death: A death occurring during the study or which comes to the attention of the investigator during the protocol-defined follow-up after the completion of the therapy whether or not considered treatment-related, must be reported.
2. Life-threatening: Any adverse therapy experience that places the subject or subjects, in the view of the investigator, at immediate risk of death from the reaction as it occurred (i.e., it does not include a reaction that had it occurred in a more serious form, might have caused death).
3. Inpatient hospitalizations or prolongation of existing hospitalization.
4. Persistent or significant disability or incapacity
5. Congenital anomaly or birth defect.
6. An event that required intervention to prevent permanent impairment or damage.

For reporting purposes only, when a participant is hospitalized for an asthma exacerbation, the date of onset of the exacerbations will be the date of hospital admission and the date of resolution will be the discharge date.

For the purposes of this protocol, a pregnancy is considered an SAE and will be reported and followed until resolution of the pregnancy with the exception of participants in the Household Asthma Sub study. Pregnancy is not an exclusion for these participants.

- d. Legal risks such as the risks that would be associated with breach of confidentiality.
The primary legal risk is breach of confidentiality. See above for description of how this risk will be minimized.
- e. Financial risks to the participants.
Prescription drugs will not be covered by the study. Prescription drugs are typically covered by health insurance. Participants are responsible for medical care if injured in this study.

8. Benefits

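### Non-serious adverse events are tracked only if judged related to study procedures, and those procedures differ by arm, so the related-only counts cannot be compared between arms (minor)

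*Combined protocol and SAP*

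**What the plan says.** Collection starts broad. Section 7.c states: "Adverse events will be documented on an individual adverse event log for each participant". No relatedness limit is attached. The items to be recorded include the "resolution status of the event, and relatedness to the study procedures".

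The later steps are narrower for non-serious events:

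- **Form (7.c):** "An adverse event form will be used for reporting all related adverse events". Serious events get an additional form.
- **Tracking (7.b):** "Related adverse events and serious adverse events, whether deemed related to study procedures or activities or not, will be tracked". The closing clause can sensibly apply only to the serious events.
- **Weekly meeting (7.b):** "which will include an update of all related adverse events and drop-outs".

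The monitoring board's remit is not narrowed: "the DSMB will meet annually to review accrual and adverse events".

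The procedures differ by arm. Under ECS Intervention in Study Procedures (3.a): "Targeted cleaning will take place at Intervention 1 and 4", and for pests, "As many as four IPM visits may occur for persistent or recurrent infestation". Pest visits for rodents include sealing cracks and holes. The Medication Group is offered the intervention only after finishing the study. Section 3.c says participants are not blinded. Section 6.c plans a disposition summary but no adverse event table, by arm or overall.

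**The concern.** A causality filter is harmless to a between-arm comparison only if it works the same way in both arms. Here it refers to study procedures, and a large part of those procedures exists in one arm only. Section 7.a says that the cleaning and caulking agents contain irritants that might provoke asthma symptoms, while calling the risk of symptoms needing emergency care very small. A mild wheeze the day after a cleaning visit has an obvious candidate cause in the ECS arm. The same wheeze in the Medication arm has none.

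A second group of events may be affected too. Section 7.a lists inhaled-steroid effects such as throat irritation and oral fungal infection. Because the relatedness field refers to procedures, it is unclear whether a drug effect counts as related. The trial's hypothesis is that the ECS lowers controller need, so fewer steroid effects would be a benefit, and a related-only count could miss it.

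At stake is the harm side of the trial's message. Section 8 says a positive result should support greater emphasis on environmental control and payer coverage. A reader weighing that needs non-serious harm counts that mean the same thing in each arm.

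**Working it through.** The plan gives no figure on this point to reproduce. The check is mainly a comparison of texts, with some counting.

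**1. Where the filter acts.**

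| Step | Non-serious events | Serious events |
|---|---|---|
| Individual log (7.c) | all | all |
| Adverse event form (7.c) | related only | additional form |
| Tracking (7.b) | related only | regardless of relatedness |
| Weekly update (7.b) | related only | not separately stated |
| Annual board review (7.b) | not limited to related | not limited to related |
| Table by arm (6.c) | none planned | none planned |

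**2. Why a related-only count is not comparable.** Let λ be the true event rate in an arm and r the probability that an event there is judged related. With equal numbers per arm,

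ratio of related-only counts = (λ_ECS / λ_Med) × (r_ECS / r_Med).

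If true rates are equal, the first factor is 1 and the ratio reduces to r_ECS / r_Med, which reflects attribution alone. The documents give no value for either r.

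**3. Procedures to which an event could be attributed during follow-up.** ECS only: up to 2 targeted cleanings (Interventions 1 and 4) and up to 4 pest management visits. Medication arm: 0 of either. Both arms share blood draws, spirometry, swabs and home visits. The count shows that r_ECS and r_Med need not be equal. It does not measure how far apart they are.

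**4. What other parts of the plan already capture without a relatedness filter.** Section 6.c compares by arm steroid bursts, hospitalizations, emergency and unscheduled visits, days of rescue use, slowed activity, exercise symptoms and cough, nights of waking, FEV1/FVC, bronchodilator response and the CASI. Symptom and medication questions look back two weeks at each clinic visit, in both arms alike. Left over are non-serious, non-asthma events, including inhaled-steroid effects, and brief asthma symptoms falling between recall windows.

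**5. What an all-event table would and would not deliver.**

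- Scheduled contacts after CV1, Medication arm: CV2, HV2, CV3, CV4, HV3 = 5.
- ECS arm: those 5 + Intervention 1 + Intervention 4 = 7. Add 1 if Intervention 3 is not on the same day as HV2, and 1 for Intervention 2 in pest-sensitised children: up to 9, before any extra pest visits.
- Ratio: 7/5 = 1.4 to 9/5 = 1.8. With equal true incidence, ECS counts could be inflated by a factor from 1.0 (reports independent of contacts) to 1.8 (reports proportional to contacts). Both ends are assumptions.
- Elicitation at CV2, CV3 and CV4 gives equal opportunity: 3/3 = 1.0.
- Precision with about 100 per arm, 95% half-width for a risk difference = 1.96 × √(2p(1−p)/100), same p in both arms (assumed range):

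| p | Half-width (percentage points) |
|---|---|
| 0.05 | 6.0 |
| 0.10 | 8.3 |
| 0.20 | 11.1 |
| 0.30 | 12.7 |

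The table can describe events but cannot support a test.

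**The case against.** The strongest reply is that little of consequence escapes the plan. The one ECS-specific mechanism that section 7.a ties to everyday events is irritation causing asthma symptoms, and symptoms are what the secondary outcomes measure, by arm and without attribution. The log is unrestricted and the board reviews adverse events with no related-only wording, so the data for a full table plausibly exist. The other ECS-specific hazards named, ingestion of rodenticide or bait, are recognisable and attributable, and a related-event form suits them. The proposed table would have its own bias from unequal contacts, and wide intervals.

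Most of this stands, and it keeps the point minor. It does not rescue the filter: the stated rule for tracking and form entry still counts non-serious events differently by arm, and no planned table corrects it.

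Several stronger readings are tempting, and the documents do not support them.

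- *Asthma symptoms that lead to no treatment or visit go uncounted.* Section 6.c compares symptom, waking and rescue-use measures by arm.
- *Only related non-serious events are ever compiled.* Neither the log nor the board's annual review is worded that way.
- *Safety data are lost for children who leave before CV2 and are replaced.* No section removes them. The log covers each participant, drop-outs are in the weekly update, a final telephone interview is attempted, and reasons for discontinuation are presented.
- *Relatedness must be judged by someone masked to arm.* The plan does not name the assessor, but that is missing detail rather than a flawed rule, and judging relatedness to a home procedure normally requires knowing that it took place.

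**Conclusion.** The concern holds as a minor one. For non-serious events, tracking, the weekly update and the adverse event form depend on relatedness to procedures that differ by arm, in a trial where families know their allocation. A between-arm difference in those counts could reflect attribution rather than incidence. Its size and direction cannot be derived from the documents. The asymmetry in attributable home procedures (up to 2 cleanings and up to 4 pest visits against 0) is a fact of the design, not a measure of bias.

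A reader might go on to infer that the efficacy results are compromised. They are not: the primary and secondary analyses do not use the relatedness judgement. The residual gap is mainly non-serious, non-asthma events and brief asthma symptoms between recall windows. The conclusion assumes that the relatedness clause in the tracking sentence extends only to serious events, which is its natural reading.

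**What to change.** In sections 7.b and 7.c, track all logged adverse events in both arms regardless of relatedness, and elicit them with the same question at CV2, CV3 and CV4. Keep the relatedness field as a descriptor rather than a gate.

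In section 6.c, add one descriptive table of all adverse events and serious adverse events by randomised arm, in all randomised children, giving number, percentage and risk difference with 95% confidence interval. Show related events as a supplement. Add a note that extra ECS-arm contacts and unblinded reporting may raise ECS counts.

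The cost is protocol wording, one question at three existing visits, somewhat more form entry and one table. The downside is more background events in that table. No visit, sample or efficacy analysis changes.
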